1 PROTOCOL SUMMARY

1.1 SYNOPSIS

Title:	Respiratory Exacerbation Plans for Action and Care Transitions for Children with Severe CP
Grant Number:	1R31HL153570-01A1
Study Description:	This study will pilot test a just-in-time adaptive intervention to reduce severe respiratory illness, for children with severe cerebral palsy (CP). Our intervention program, called RE-PACT, delivers timely, customized action planning and health coaching when mobile text messaging with families predicts hospitalization risk is elevated. The study period will be divided into three waves: after each wave, feasibility, acceptability, and fidelity data will be reviewed against pre-defined measures of success to adjust the protocol and overcome implementation barriers.
Objectives*:	
Primary Objective: To establish feasibility, acceptability, and fidelity of RE-PACT in 90 children with severe CP.
 
Secondary Objectives: To establish effect size of RE-PACT.

Endpoints*:	
Primary Endpoint: The primary outcomes are pre-defined measures of feasibility, acceptability and fidelity of targeting RE-PACT and/or assessments to children with severe CP
 
Secondary Endpoints: The primary clinical outcome is severe respiratory illness, defined as respiratory diagnosis requiring hospitalization. Additional secondary clinical endpoints include: total hospital days during severe respiratory illness, numbers of systemic steroid courses, systemic antibiotic courses, respiratory ED visits, and death

Study Population:	This intervention will recruit primary caregivers of children with severe CP. A total of n=90 caregivers of children with severe (GMFCS level V) CP, ages 0-17 years and cared for by a respiratory specialist or receiving daily respiratory treatments will be enrolled. Caregivers will be at least 18 years of age and have a phone capable of sending/receiving text messages. Subjects will speak English or Spanish. There are no additional demographic enrollment criteria. Participants will be recruited from pediatric complex

care programs at the University of Wisconsin-Madison (UW) and the University of California, Los Angeles (UCLA).

Phase* or Stage:

Behavioral Health Intervention Study

**Description of Sites/
Facilities Enrolling
Participants:**

The two-site study takes place at clinical programs at US children's hospitals: the UW and UCLA Pediatric Complex Care Programs were each established to deliver care to children with medical complexity. Each program is comprised of primary care providers, care coordinators, and extended visit lengths, deliver comprehensive care to children with cerebral palsy. These sites have existing collaborative relationships through their participation in the CYSHCNet national research network (<http://cyshcnet.org>) and other federally funded initiatives, and a track record of successful productive scientific collaboration.

Description of Study Intervention/Experimental Manipulation: The study period will be divided into three waves: after each wave, feasibility, acceptability, and fidelity data will be reviewed against pre-defined measures of success to adjust the protocol and overcome implementation barriers.

This study will be conducted through a six-month randomized pilot trial. Briefly, after recruitment and baseline assessments, eligible caregiver/child dyads are randomized to intervention (I) or active control (AC). Intervention subjects receive respiratory illness action plans and weekly mobile health (mHealth) confidence surveillance. At times of low confidence or hospitalization, just-in-time action planning and coaching activities are conducted. AC subjects will receive usual comprehensive medical care and coordination. Assessments of feasibility, acceptability and fidelity, as well as clinical outcomes, will be conducted at baseline and monthly intervals for 6 months. Intervention outcomes will be evaluated at baseline (i.e., randomization) and 6 months post-enrollment, and will also include the primary clinical outcome (i.e., hospitalization for respiratory diagnosis).

[figure not shown]
Study Duration*:

24 months

Participant Duration:

6 months

1.2 SCHEMA

1.3 SCHEDULE OF ACTIVITIES

	STUDY PERIOD							
	Enroll- ment Visit	REPACT Intervention Period						Final Visit
Personnel involved	Research Coordina- tor	Clinicians						Research Coordina- tor
Month	0	1	2	3	4	5	6	End of Month 6
Timepoint	T ₀	T ₁	T ₂	T ₃	T ₄	T ₅	T ₆	T ₇
Confirm eligibility	X							
Informed Consent	X							
Baseline Assessment	X							
6-month Assessment								X
Randomization	X							
Subject Payment	X							X
Usual comprehensive medical care and coordination via Complex Care Program		X	X	X	X	X	X	
Intervention Arm Only								
Text Msg Training	X							
Weekly mHealth text message and response		X	X	X	X	X	X	
Intervention overview		X						
Create action plan		X						
Action planning		X	X	X	X	X	X	
JIT coaching		X	X	X	X	X	X	
Monthly study assessments		X	X	X	X	X	X	

2 INTRODUCTION

2.1 STUDY RATIONALE

Respiratory illnesses, including aspiration, pneumonia, and respiratory failure, are devastating to children with severe cerebral palsy (CP). Respiratory illness is the number one cause of hospitalization and death in children with severe cerebral palsy (CP). CP is the most common motor disability in US children, and children with CP have 26x higher medical costs than those without, averaging >\$1.3M per child in lifetime care costs. We define severe CP as spastic quadriplegia, i.e., no independent mobility (gross motor function classification system level V). Little progress on respiratory outcomes in CP has occurred in the last 40 years.

Severe respiratory illnesses, which we define as respiratory diagnoses requiring hospitalization, are considered potentially modifiable in CP. Families are first in line to manage these challenging events because the illness emerges at home. However, respiratory care routines are especially difficult for families in the setting of limited support to bolster knowledge, skills, and confidence. To bridge this gap, parents need clinical teams to provide the right support, at the right time, in the right context, i.e., just-in-time and adaptive.

Just-in-time adaptive interventions (JITAI) hold promise to help children with CP with respiratory illness. Our behavioral intervention, Plans for Action and Care Transitions (PACT) combined action planning with caregiver coaching and reduced all-cause hospitalizations for children with complex diseases including severe CP. Although PACT's action plans gave families just-in-time options to manage crises, plans were pre-specified, static, and did not adjust to real-time issues. To prevent severe respiratory illness in CP, responses must be dynamic, and address the wide array of contexts and comorbidities that drive these episodes. Simultaneously, clinicians and families need very simple tools that signal when they need help.

Mobile health (mHealth) approaches linked to clinical teams can easily indicate when families of children with CP experiencing respiratory illness need help. Meta-analysis of mHealth interventions suggests improved disease control in children, particularly when directed to caregivers. In early-stage studies of asthma and COPD, mHealth monitoring / response systems are associated with fewer exacerbations. We will integrate an mHealth texting solution with PACT to trigger our just-in-time adaptive intervention for severe CP. The objective of this study is to finalize a feasible, acceptable, and high-fidelity adaptive intervention, and to determine expected effect sizes for reducing severe respiratory illness for a fully powered trial. Completion of the study is necessary to subsequently conduct an adequately powered multisite efficacy trial.

2.2 BACKGROUND

Cerebral palsy (CP) is the leading cause of motor disability in childhood^{8,9} and has grave respiratory consequences.¹³ CP is caused by damage to the developing brain that permanently disrupts the ability to

control movement and maintain posture. Children with severe CP have spastic quadriplegia (i.e., all four extremities affected) and level V gross motor function classification system [GMFCS] (i.e., no independent mobility). Mechanisms of respiratory illness in severe CP parallel those of other neuromuscular diseases,²⁷ examples include respiratory muscle weakness, recurrent infections and aspiration with inflammatory fibrosis, impaired airway clearance from altered tone, upper airway abnormalities and poor chest wall compliance.^{28,29} CDC estimates >\$16B in lifetime cost for the children with CP born in 2000 alone.¹⁰

Respiratory illness is consistently the #1 cause of death and hospitalization in severe CP.^{4,30} Only 33% of children with CP and four co-occurring disabilities survive to age 30.³¹ Respiratory illness accounts for 59% of deaths^{3,4} and 25% of hospitalizations^{1,7,8} in severe CP. Moreover, respiratory illness strongly predicts future episodes; respiratory hospitalization risk is 10-fold higher with a respiratory illness in the past year.¹⁴ In fact, over 20% of hospitalizations are followed by another within 30 days and nearly 70% in the next year.⁷ Hospitalizations for respiratory illness are 76% costlier⁸ and 2.5 times longer for children with severe CP than those without.¹⁴ Prevention of these events is a significant need, and a key to improving quality of life and mortality.^{6,13} Though the respiratory illness risk factors in severe CP are considered modifiable,¹⁴ and despite investments in respiratory care, little improvement in these outcomes has occurred in CP in 40 years.^{1,2,8}

The very high utilization and specialized needs of parents of children with severe CP demands unique solutions (Box 1). In a 2007-2014 population-based child cohort with severe CP, over 91% had ≥ 1 hospitalization (median [IQR], 4 [2-8]).⁸ Unlike children with single system disease, such as asthma, those with severe CP are 100% dependent for every activity of daily living, cannot communicate, and have subtle illness signs. Families must monitor high-acuity comorbid conditions and administer elaborate care plans despite concerns that they lack preparation and tools to deliver this sophisticated care at home.^{6,13,15,32-35} Parents of children with CP articulate the need for interventions focused on crisis management and self-efficacy.^{7,15,36}

Preventing hospitalization requires the opportunity for families and clinical teams to connect early enough to change trajectory.^{15,16,37} Not knowing when just-in-time care is needed is a current barrier to effective action planning and health coaching in complex illnesses. Concerns may not reach clinical teams until an ED visit or hospitalization is inevitable. Families need their clinical teams to respond to early discomfort.³⁸ In fact, a national expert panel to identify interventions to prevent hospitalization of children with complex diseases³⁹ concluded that enhanced access, proactive crisis planning, and support for caregiver technical skill were key strategies to lower hospital use. Prior post-discharge research confirmed that when parents were not confident that their child with chronic conditions could avoid hospitalization or ED visit, admissions and ED visits within weeks were predicted better than by other clinical or demographic indicators.^{40,41} Preliminary work with a cohort including children with severe CP demonstrated that parent confidence, monitored prospectively and repeatedly by text message is feasible, acceptable and predicts hospitalization within 2 weeks. Being able to target rapid “just-in-time”, customized, clinical response to periods of low parent confidence, before respiratory illness becomes crisis, is a key advance of this research.

Preventing Respiratory Illness in Severe CP Requires Broad, Adaptive, Timely Intervention. Action planning and health coaching are effective strategies in other populations. For example, from 2003 to 2013, hospitalization rates for pediatric asthma dropped by half (from 9.6% to 4.7%), during which time asthma action plan use increased significantly.⁴² A family intervention linking home-based asthma coaching to action planning significantly reduced hospitalizations in poorly controlled asthma.⁴³ However, respiratory illness in severe CP has broad comorbid triggers, e.g., emesis, dysphagia, aspiration, seizures, among others. Simple action plans or coaching alone cannot address the breadth of respiratory illness triggers or potential responses. For example, if a parent of a child with severe CP follows an action plan directed towards bronchospasm, it would not effectively address an acute infectious lower respiratory infection. Parents of children with severe CP need action plans and coaching, but they also need an efficient direct extension to their clinical team for adaptive, just-in-time clinical response directed specifically to real-time acute problems.

The Plans for Action and Care Transitions (PACT) intervention was developed by this team to prevent hospitalizations for children with complex chronic diseases including severe CP. After integrating systematic literature review,⁴⁴ parent interviews,³⁸ and a national expert panel,³⁹ each focused on preventing hospitalization, PACT was designed to leverage evidence-based strategies from different populations: asthma action planning,⁴⁵⁻⁴⁷ health coaching,⁴⁸⁻⁵⁰ and feedback at our Parent Advisory Group's monthly meetings. PACT delivered action planning and coaching activities to children with diverse complex diseases, including severe CP, and a PACT RCT found 40% lower hospitalization rates for intervention vs control patients.¹⁸

The purpose of this study is to achieve protocol revisions and preliminary data to support a large multisite RCT to reduce respiratory illness in severe cerebral palsy. This study adapts the efficacious PACT intervention into "Respiratory Exacerbations-PACT" (RE-PACT) for children with severe CP. The proposed research is significant because the intervention targets the central, yet currently overlooked, cause of severe respiratory illness in severe CP – under-supported families managing emerging health crises at home. RE-PACT links an innovative just-in-time adaptive response to an effective intervention developed by this team. RE-PACT delivers the right care, at the right time, in the right context. The RE-PACT intervention platform has direct potential to accelerate the translation of discovery into practice by embedding a research platform within 'learning' health systems, thereby engaging clinical care and patient communities; and creating an integrative interface between research and practice. This study will establish feasibility, acceptability, and fidelity, and determine likely effect sizes of the intervention to reduce respiratory illness in severe CP. Successful completion of these objectives, will build a strong scientific foundation and necessary data, infrastructure and protocols to conduct a full-scale efficacy trial.

2.3 RISK/BENEFIT ASSESSMENT

2.3.1 KNOWN POTENTIAL RISKS

The proposed research will pose minimal risks to human research subjects, comparable to the risks incurred through everyday conversations, routine visits with clinic providers, and basic psychological tests. The potential risks are immediate risks (not long-term) and include: 1) mild psychological discomfort in discussing parenting, personal and family matters, including challenges and demands about caring for a child with severe disabilities, and family socio-demographics, including parental education and household income; 2) social risk by participating in the study, if their participation were to become known to anyone outside the research team; and 3) loss of confidentiality.

One potential long-term risk is that if families feel a false sense of security during an illness (e.g., from their coaching experience), they may seek care later and present with a more advanced or potentially severe acute illness. This risk is minimized however, by having clear protocols for coaches to follow to include clinical team members, and not restricting families from using their usual support channels when their child is ill (e.g., calling their provider, having an urgent visit in clinic, going to the emergency room, etc.).

2.3.2 KNOWN POTENTIAL BENEFITS

The potential benefits are immediate. All participants will receive information about their child's health status (such as care recommendations and the results of clinical tests and procedures), which may benefit families with or without concerns, and in part ameliorate the psychological risk posed by the research. Clinical information will be exchanged by oral communication between the parent and the Peds Complex Care clinical team member. The clinical team member may also communicate (orally or by MyChart) with other members of the child's clinical team (such as their pulmonologist and other specialists). Such communication is part of the standard care provided for families in the Pediatric Complex Care Program. For families enrolled in the randomized clinical trial, study staff will also share information about parent confidence with clinical providers. For example, if a parent reports low confidence that their child will avoid hospitalization in the next month, the clinical team member will share this information with other members of the child's care team to determine whether changes in care are recommended. As always, the clinical team member will discuss parental confidence, parental opinion of their child's care plans, and/or parental opinion of their child's providers with professionalism and sensitivity to patient-provider relationships. They will divulge the minimum amount of information needed to discuss the patient's health status.

The potential benefit of REPACT is that early communication will lead to early detection of crises (respiratory or otherwise) and opportunities for early intervention. It is unclear what the benefits of the RE-PACT intervention will be to study participants, but there is a potential benefit of preventing hospital and emergency department use, and improving experiences navigating the health system. There is also a potential benefit to providers in having RE-PACT help with care coordination (e.g., knowing who and when to call for respiratory health problems).

2.3.3 ASSESSMENT OF POTENTIAL RISKS AND BENEFITS

Rationale for the necessity of exposing participants to risks: If proven effective for families and providers, the proposed RE-PACT intervention has the potential to help many families and clinical systems in the future. Developing more streamlined and effective processes for real-time identification of health crises and linking families with “just-in-time” clinical interventions has the potential to improve systems of care for vulnerable children and their families, ultimately with the potential to improve health outcomes.

Summary of the ways that risks to participants were minimized in the study design: Participation in the study will be completely voluntary and participants may end their participation at any point.

Participation in the study should not affect the routine medical care they receive. Clinical providers will be notified of screening results for all participants. Participants may decline to participate in any given component of the study and may decline to answer any particular question they do not wish to answer. Their participation in the study will remain confidential, with meetings between study staff and participants happening in private rooms. Written questionnaires will be labeled with a unique identifier and other identifying information will not be associated with written data. Any identifying information kept for the purposes of contacting participants will be kept secure, in REDCap, a locked filing cabinet or in a password-protected electronic file and will be destroyed when the study is complete. In the event of any adverse events, we will follow the protocols as described in the data safety monitoring plan, including notification of the PI and Co-I (UCLA site PI), clinical escalation as appropriate using the clinical staff in the respective clinic partner sites, and notification of authorities as required by law (Child Protective Services and/or law enforcement).

Justification as to why the value of the information to be gained outweighs the risks of participation in the study: This platform may prove to be adaptable to other disease states which experience acute exacerbations managed (at least in part) by families at home. Many of these improved processes are yet to be developed and tested. This study would add to the knowledge about what is effective, possibly leading to important future research and implementation efforts.

3 OBJECTIVES AND ENDPOINTS

OBJECTIVES	ENDPOINTS			JUSTIFICATION FOR ENDPOINTS	PUTATIVE MECHANISMS OF ACTION
Primary					
To establish feasibility, acceptability, and fidelity of RE-PACT in 90 children with severe CP.	MEASURES	MEASURE DETAIL	SUCCESS DEFINITION		
	FEASIBILITY		n=90		
	Recruitment	Days to enroll target, mean	<14		
	Intervention onset	Days between randomization and “time zero” intervention activities, mean	<7		
	Intervention time	Time logged (minutes) for action planning and for coaching activities, mean			
	Intervention costs	Mileage / travel costs; Personnel salary; Training; Other incurred costs, total			
	Intervention triggers	Number per patient (annualized); respiratory and non-respiratory focused			
	Data infrastructure	Data collection reliability; Coordination at UW, Data use agreements / IRBs			
	ACCEPTABILITY				
	Enrollment	Enrollment rate (# of patients enrolled / # approached)	>80%		

OBJECTIVES	ENDPOINTS			JUSTIFICATION FOR ENDPOINTS	PUTATIVE MECHANISMS OF ACTION
	Consent refusal	Categorized reasons for refusal			
	Loss, Drop out	Rate of drop out (active or passive) before 6 months (# drop out / # enrolled)	<10%		
	Action plan, Coaching, texting satisfaction	Do caregivers use the action plan, coaching and texting (why / why not); How could it be improved; Would caregivers recommend this to another family? (why / why not)			
	FIDELITY				
	Enrollment duration	Time (months) of participant enrollment in the study, mean	6		
	Action plan creation	# respiratory and overall action plans per patient; Action plan focus areas	≥1		
	Coaching – home or virtual visit	Success rate (# visits completed / # expected); stratify by trigger (hospitalization vs confidence rating)	>80%		

OBJECTIVES	ENDPOINTS			JUSTIFICATION FOR ENDPOINTS	PUTATIVE MECHANISMS OF ACTION
	Coaching – phone calls	Success rate (# phone calls completed / # expected); stratify by trigger (hospitalization vs confidence rating); respiratory and non-respiratory	>80%		
Secondary					
To establish effect size of RE-PACT.	Severe respiratory illness, defined as respiratory diagnoses requiring hospitalization. Respiratory diagnoses includes discharge diagnosis of any of the following: asthma, pneumonia (community or hospital acquired), bronchiolitis, influenza, upper or lower respiratory tract infection,				

OBJECTIVES	ENDPOINTS	JUSTIFICATION FOR ENDPOINTS	PUTATIVE MECHANISMS OF ACTION
	tracheitis, aspiration pneumonia/pneumonitis, chronic lung disease, respiratory failure.		
Tertiary/Exploratory			
To explore the mediating relationships between RE-PACT and capability, opportunity, motivation (COM-B) measures.	Capability : Family Caregiver Activation in Transition Measure (FCAT)117 – mean composite score Caregiver General Self-Efficacy Scale (GSES) 118 – mean composite score. Opportunity : Family Experiences with Care Coordination (FECC)119 - % top-box score for selected items Motivation : Confidence Responses mHealth texting (weekly score 1 through 10)	Blending our foundational research on preventing hospitalizations, ^{38,39} with behavioral intervention theory, ¹¹³ our conceptual model suggests that decisions to seek care (behaviors) are influenced by capability (family capacity), opportunity (health system and susceptibility), and motivation (confidence). Confidence is a modifiable expression of self-efficacy to achieve an outcome, i.e., to avoid hospitalization and manage (respiratory) crisis at home.	A theorized mechanism of RE-PACT's effect is that the combination of action planning, mHealth surveillance, and coaching, will increase caregiver capability, opportunity, motivation to manage respiratory illness in severe CP.

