RE-PACT involves action planning and health coaching to prevent and manage respiratory illness, as well as weekly text messaging surveillance of caregiver confidence for their child to avoid a hospitalization. All intervention families will receive respiratory illness action plans at study entry. Action plan content will be consistent with standard clinical care guidelines and will not differ from the recommendations of the child's clinical care team. Health coaching focuses on managing medications, understanding and responding to red flags, keeping patient-centered records, maintaining timely follow-up with primary or specialty care. Coaches focus on skill transfer to parent caregivers, achieved through structured face-to-face or virtual telehealth coaching and phone follow-up over a 2-week period. Just-in-time action planning and coaching activities are triggered by caregiver text message responses indicating low confidence (rating ≤ 4 on 1-10 scale) to avoid a hospitalization. The usual care, active control group will continue to receive comprehensive care coordination and medical management.

Study participants will be randomly assigned to receive usual care through the complex care clinical program, or the study intervention, RE-PACT. Random allocation will be concealed to research staff conducting recruitment and will use a 1:1 allocation with random block sizes of 2 and 4. Block randomization will be achieved with a computer-generated random number list prepared by the study

biostatistician having no clinical involvement in the trial. Randomization will be stratified by site to account for site-specific study characteristics.

RE-PACT will be run through three successively larger 6-month trials (“waves”), allowing ongoing protocol refinement according to pre-specified definitions of success for measures of feasibility, acceptability and fidelity. Each wave has a specific protocol refinement focus: Wave 1 – onboarding/training, recruitment, data collection; Wave 2 – randomization and intervention activities; Wave 3 – rapid enrollment and conducting all protocol activities with high-fidelity.

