6.1.2 ADMINISTRATION AND/OR DOSING

mHealth Surveillance. Text messages are programmed to be sent at random days / times to caregivers beginning the Monday after enrollment. Text messages average once weekly (Sun-Thurs) between 8AM and 9PM (local time). After 2 hours of non-response, a reminder is sent, and this is repeated up to 2 times.

Action Planning. All intervention families receive respiratory illness action plans within 1 month of study entry, and just-in-time plans are also created at times of low confidence. Plans are created in caregivers' preferred language (English, Spanish) by physician or nurse practitioner using our protocol (see intervention manual). After plans are created, teach-back is used. Copies are given to families and included in medical records. Plans are discussed at weekly clinical meetings for clarity and accuracy.

Just-in-time Adaptive Coaching Intervention Response. In the original design, coaches met families prior to a hospital discharge, conducted face-to-face visits within 72 hours and 3 phone calls within 30 days, post-discharge. Compared to the original PACT design, RE-PACT was adapted to trigger just-in-time adaptive intervention (JITAI) action planning and coaching doses when caregiver text message responses indicate low confidence. JITAI action planning and coaching doses occur within 24 hours of any text message ratings ≤ 4 . This confidence threshold to trigger JITAI and the text prompt wording was vetted in preliminary qualitative research with families and clinicians and is based on our prospective pilot study at UW and UCLA whereby confidence ratings ≤ 4 predicted hospitalizations a median (IQR) 8 (2-10) days in advance. The protocol currently supports intervention coach credentials to include undergoing coach training (or equivalent, see intervention manual), and individuals can possess any university degree of higher. For example, a coach could be a care coordinator with a bachelor's degree, a physician, or other health professional.

The study feasibility, acceptability and fidelity measures are designed to quantify intervention doses, dose intensity and frequency (e.g., # of coach visits, # of action plans), and include incomplete dose administration (e.g., poor text message response rates).

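### The fidelity criteria do not test the 24-hour response that defines the just-in-time intervention, and the routine entry plan alone satisfies the action-plan criterion

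*Combined protocol and SAP*

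**What the plan says.** **Delivery rule.** Section 6.1.2 states that "JITAI action planning and coaching doses occur within 24 hours of any text message ratings" of 4 or less. It supports the threshold with a pilot in which such ratings "predicted hospitalizations a median (IQR) 8 (2-10) days in advance".

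**Entry plan.** Section 4.1 says "All intervention families will receive respiratory illness action plans at study entry". Section 6.1.2 says "All intervention families receive respiratory illness action plans within 1 month of study entry, and just-in-time plans are also created at times of low confidence". Triggered plans are thus additional to a plan that every intervention family gets anyway.

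**Success definitions in Section 3 that concern delivery:**

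- Action plan creation (fidelity): "respiratory and overall action plans per patient; Action plan focus areas", success at least 1.
- Coaching, home or virtual visit (fidelity): "Success rate (# visits completed / # expected); stratify by trigger (hospitalization vs confidence rating"), success above 80%.
- Coaching, phone calls (fidelity): "Success rate (# phone calls completed / # expected); stratify by trigger (hospitalization vs confidence rating); respiratory and non-respiratory", success above 80%.
- Intervention onset (feasibility): "Days between randomization and “time zero” intervention activities, mean", success below 7.
- Intervention time (feasibility): minutes logged, no threshold.

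**Use of the criteria.** Section 8.1 has the measures summarized between waves, with the protocol adjusted where one falls short. Section 6.2.1 logs how many action plans were made and when. Section 9.4.2 plans to compare observed with expected performance for each component, including the just-in-time coaching response. None of these sets a standard for response time.

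**The concern.** Fidelity is one of the three parts of the primary objective. Timing is also what distinguishes RE-PACT from its predecessor: Section 2.1 describes the earlier PACT plans as fixed in advance, and Section 2.2 presents a quick response to low confidence, before illness becomes a crisis, as a key advance. A fidelity assessment of this intervention should be able to fail when the response is late or when no triggered plan is made.

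As written, it may not. The pilot could meet every fidelity target and take its protocol forward to the multisite trial without having tested whether teams can respond within the stated time. The lower quartile of the pilot lead time, 2 days, shows why the interval matters: in about a quarter of the hospitalizations described, the low rating came 2 days or less beforehand.

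**Working it through.** The targets (at least 1, above 80%) are choices and not derived figures, so there is no plan calculation to reproduce. The check sets the passages side by side and then shows by a small calculation what the coaching ratio can and cannot detect.

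**1. Is any delay after a trigger scored?** The only delay threshold on intervention delivery is intervention onset, which runs from randomization to the start-up activities. It ends before any trigger response begins. Intervention time measures minutes spent, not minutes elapsed. No Section 3 row measures the interval from a low rating to the response.

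**2. Action-plan row.** Let E be the number of entry plans for a family and J the number of just-in-time plans. The criterion is E + J ≥ 1. If the entry plan is delivered as Sections 4.1 and 6.1.2 intend, E = 1. With J = 0 the total is 1 + 0 = 1, and the criterion passes. The number of triggers is recorded per patient but has no threshold and is not linked to the number of plans.

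**3. Coaching rows.** The measure is completed contacts divided by expected contacts, and elapsed time does not enter it. Section 3 defines neither term, so the text does not say that a contact after 24 hours stops counting.

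**4. Illustration.** Assumptions that the documents do not give: N expected contacts, each completed with probability 0.90, independently; a share q of completed contacts falls within 24 hours; the ratio is read literally, with no window.

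- Passing means more than 80% of N: at least 17 of 20, 41 of 50, or 81 of 100.
- As written, P(pass) = P(X ≥ threshold), X ~ Binomial(N, 0.90). This does not contain q.
- With the 24-hour rule in the numerator, X ~ Binomial(N, 0.90 × q).

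| N | As written, any q | Timed, q = 1.0 (rate 0.90) | Timed, q = 0.9 (rate 0.81) | Timed, q = 0.8 (rate 0.72) | Timed, q = 0.6 (rate 0.54) |
|---|---|---|---|---|---|
| 20 | 86.7% | 86.7% | 45.6% | 14.7% | 0.4% |
| 50 | 97.5% | 97.5% | 51.5% | 7.4% | <0.1% |
| 100 | 99.8% | 99.8% | 56.1% | 2.6% | <0.1% |

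For the timely rate to exceed 0.80 at 90% completion, q must exceed 0.80 / 0.90 = 0.889.

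**5. Consequence for the waves.** By steps 1 to 4, a late response that is eventually completed leaves all three delivery criteria where they were. The Section 8.1 rule, which acts on measures that miss their definition, is then not activated by lateness alone.

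**The case against.** The strongest reply is that *# expected* is undefined. Since Section 6.1.2 places the dose within 24 hours, an expected dose could be read as a dose inside that window. The intervention manual, cited but not among the documents, or the detailed SAP that Section 9.4.1 says is still to be finalized, might say so. This stands as a limit: that late contacts count is an inference from the missing window, not something the plan states. It does not help the action-plan row, where the stated rule passes without any triggered plan.

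Second, lateness could surface elsewhere. Plan dates are logged, components are compared with expectation, clinical teams are debriefed between waves (Section 8.1), and participant feedback informs design changes (Section 9.1). That is true, and it softens the consequence, but none of these routes has a pre-specified standard. Several Section 3 rows are deliberately descriptive; the coaching and plan rows are not, since they carry targets.

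Third, the binomial figures rest on assumed inputs and only show that a ratio without timing ignores timing. That is accepted; they are an illustration, not a forecast.

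A reader might infer more in two ways:

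- *That about half of the contacts would come too late, by setting the 8-day median lead time against visits made around day 8.* The documents give no distribution of contact delays. The lead times concern hospitalizations generally, in an earlier pilot. Hospitalization is itself a coaching trigger in Sections 3 and 6.1.1, and Section 4.1 spreads coaching and phone follow-up over two weeks, so a contact in the second week may be a scheduled one.
- *That the effect size passed to the larger trial is diluted.* Nothing in the documents quantifies or shows late delivery, and rescoring fidelity changes delivery only if it prompts an adjustment.

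**Conclusion.** The gap is real and should be closed. It has two parts of different firmness. The action-plan criterion can pass with no just-in-time plan; this follows directly from Sections 3, 4.1 and 6.1.2, given that entry plans are delivered. The coaching ratios do not separate prompt from late response as written; this assumes that no definition outside these documents restricts what counts as completed or expected.

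It would be too strong to say that triggered coaching goes untested: its completion is tested, by trigger, against 80%. What lacks a threshold is its timeliness, and whether a plan followed a trigger. The 24-hour statement covers text ratings only. For coaching after hospitalization, Section 6.1.2 gives times only for the original PACT design, so no RE-PACT window exists to score.

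The practical size is that late response alone moves no measure below its success definition, on a primary outcome that drives between-wave adjustment.

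**What to change.** 1. Add a fidelity row for text-triggered episodes: the proportion with a first just-in-time coaching contact within the protocol's own 24 hours. The sponsor should specify whether a visit, a call or either is the contact that counts, since Section 4.3 lets the form of response vary. Pre-specify a target, for example the 80% already used, and report the trigger-to-response time.
2. Keep the any-time completion ratios for visits and calls, and define *# expected* for each trigger.
3. Split the action-plan row into (a) the proportion of intervention families with an entry plan within the 1 month stated in Section 6.1.2, and (b) the proportion of text-triggered episodes with just-in-time action planning within 24 hours, with a target pre-specified by the sponsor. Sections 4.1 and 6.1.2 describe the timing of the entry plan differently, and the intervention-onset target is a mean below 7 days; these need reconciling first.
4. For hospitalization-triggered coaching, report timing descriptively. The sponsor should reconcile the passages: Sections 3 and 6.1.1 name hospitalization as a trigger, while Section 4.2 says that only text responses trigger coaching.

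**Cost.** Mostly wording in Section 3 and the SAP. Text logs already exist. Section 6.2.1 lists when plans are created but not coaching contact times, and a 24-hour test needs times as well as dates, so a date-and-time field may have to be added to the study log. The fidelity figures may look less favourable.
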